5.4 Demography and Other Baseline Characteristics

Baseline and demographic information (age, ethnicity, race, height, weight at baseline, body mass index [BMI] at baseline, Eastern Cooperative Oncology Group [ECOG] at screening) will be listed and summarised. For continuous variables, the summary will consist of descriptive statistics (number of participants, mean, SD, minimum, median, and maximum). For categorical variables, the summary will consist of number and percentage of participants in each category.

All demographic and baseline characteristics summaries and listings will be provided for the SAF set. No statistical comparison will be performed.

Following summaries will be provided on:

- Demographic variables (refer to [Appendix 5](#) for European Union Drug Regulating Authorities Clinical Trials Database [EudraCT] age categories),
- Prostate cancer history and disease characteristics (time from histological diagnosis to screening, TNM Classification of Malignant Tumors [TNM] Stage, PSA and Testosterone from central lab at Baseline).

Listings will also be provided for all the summaries listed above.

5.5 Medical History, Non-Drug Therapies, Medications and Surgical Procedures

Medical and surgical history, non-drug therapies and surgical procedures will be coded using Medical Dictionary for Regulatory Activities (MedDRA). Medications will be coded using World Health Organization-Drug dictionary.

Medication, non-drug therapies and surgical procedures start and stop dates will be compared to the date of the first IMP administration to allow classification as either Prior only, Prior and Concomitant, or Concomitant only:

Prior (P)	Start and stop dates prior to the date of the first IMP administration.
Prior and Concomitant (PC)	Start date before the date of the first IMP administration and stop date on or after the date of the first IMP administration.
Concomitant (C)	Start date on or after the date of first IMP administration.

Summary tables on prior medications/non-drug therapies/surgical procedures will include “P” and “PC”, and summary tables on concomitant medications/non-drug therapies/surgical procedures will include “C” and “PC”.

Rules for classification of prior and concomitant medication/non-drug therapies, surgical procedures in case of partial/missing date are detailed in [Appendix 2](#).

Associated Procedure / Instruction Reference	319480-SOP
Form Reference	080091-FOR v7.0

Medical history and concurrent medical conditions will be summarised by system organ class (SOC) and preferred term (PT). Medication history and concomitant medications will be summarised by Anatomical Therapeutic Class (ATC) code and preferred name (PN). The therapeutic class will correspond to the second level of ATC code, that is, corresponding to the first three figures.

Following summaries, presenting count and percentages of participants will be provided on the enrolled set:

- Medical and surgical history by SOC and PT,
- Prior medications for the studied disease by ATC class and PN (ATC level 2),
- Prior radiotherapies for cancer by primary SOC and PT,
- Prior surgical procedures for the studied disease by primary SOC and PT,
- Concomitant surgical procedures by primary SOC and PT,
- Prior medications by ATC class and PN (ATC level 2),
- Concomitant medications by ATC class and PN (ATC level 2),
- Prior non-drug therapies by primary SOC and PT,
- Concomitant non-drug therapies by primary SOC and PT.

Listings will be provided for prior and concomitant medication/non-drug therapies, and surgical procedures. These listings should include a flag indicating the category (P, PC, C) as described in the table above.

5.6 Compliance

The compliance will be calculated as defined in section [7](#).

Following summary and listing will be provided on the safety set:

- Descriptive statistics of compliance including number of percentage of participants by compliance category (<50%, 50 - <70%, 70 -<90%, 90-100%),
- A listing of treatment compliance.

5.7 Efficacy

5.7.1 General Considerations

The FAS set will be used for efficacy analyses unless explicitly stated differently.

A listing of all efficacy data (raw and derived) will be provided (see listing detail conventions in [Appendix 4](#)).

5.7.1.1 Significance Testing and Estimations

The statistical analysis of efficacy is only descriptive therefore no formal statistical significance testing will be performed.

Associated Procedure / Instruction Reference	319480-SOP
Form Reference	080091-FOR v7.0

5.7.1.2 Handling of Dropouts and Missing Data

Completely missing data are generally not imputed. Partial missing start and end dates will be imputed for medication category and treatment-emergent adverse event (TEAE) determinations. Details are provided in the [Appendix 2](#).

5.7.1.3 Statistical/Analytical Issues

Adjustments for Covariates

Covariates adjustment is not applicable to this study.

Interim Analyses and Data Monitoring

See section 3.

Multicentre Studies

This is a multicentre study conducted in seven countries (Belgium, Czech Republic, France, Germany, Lithuania, Netherlands, Spain). Due to the limited sample size, this is an open-label study, no adjustment for centre effects is planned for this study.

Multiple Comparisons/Multiplicity

No formal testing will be performed in this study and multiplicity adjustment is not applicable.

5.7.2 Analysis of Primary Efficacy Endpoint

5.7.2.1 Primary Efficacy Endpoint, Treatment Effect and Estimand Definition

To assess the primary objective, the primary estimand will be defined by the following attributes:

- Population: participants with locally advanced and/or metastatic prostate cancer previously treated and castrated with a GnRH analogue as defined by the listed Inclusion/Exclusion criteria in sections 5.1 and 5.2 of the protocol, respectively.
- Variable/Endpoint: castration maintenance rate during the study defined as percentage of participants castrated (testosterone < 1.735 nmol/L (50 ng/dL)) at Day 29, Day 85, Day 141, Day 169, Day 253, Day 309 and Day 337, with two complete study intervention administrations.
- Key Intercurrent event (ICE):
 - (a) ICE 1 - Subjects discontinued from study prior to Day 337 without evidence of inadequate testosterone suppression (testosterone measurement \geq 50 ng/dL)
The testosterone values of these participants will not be considered for the main analysis (principal stratum strategy).
 - (b) ICE 2 - Subjects with at least one planned testosterone measurement missing on or prior to Day 337 without evidence of inadequate testosterone suppression (testosterone measurement \geq 50 ng/dL)
The testosterone values of these participants will not be considered for the main analysis (principal stratum strategy).

Associated Procedure / Instruction Reference	319480-SOP
Form Reference	080091-FOR v7.0

(c) ICE 3 - Subjects discontinued treatment prior to receiving the second study intervention administration without evidence of inadequate testosterone suppression (testosterone measurement ≥ 50 ng/dL)
The testosterone values of these participants will not be considered for the main analysis (principal stratum strategy).

(d) ICE 4 - Subjects received a prohibited medication during the study
Prohibited medication with impacts on the testosterone value will be identified through blinded data review. Subjects receiving identified prohibited medication (for example, finasteride, dustasteride, or abiraterone) will be included in the primary analysis as non-responder. In contrast, all testosterone measurements from subjects receiving prohibited medications other than identified ones during the study will be included in the primary analysis (composite strategy).

- Treatment regimen: triptorelin 6-month formulation administered subcutaneously and potential intake of permitted concomitant medications (for a list, see protocol section 6.3)
- Population-level summary of the treatment effect of interest: percentage of participants with a castration maintenance.

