4 STUDY DESIGN

4.1 Overall Design

This is a phase III, multicentre, open-label, non-comparative, repeat dose study to evaluate the efficacy and safety of triptorelin 6-month formulation (22.5 mg) administered subcutaneously in participants with locally advanced and/or metastatic prostate cancer previously treated and castrated with a GnRH analogue.

Approximately 145 participants will be assigned to triptorelin embonate 22.5 mg (6-month formulation) to be administered on Day 1 and Day 169. Note: participants must receive study intervention on Day 1 in accordance with the treatment schedule of their previously received GnRH analogue therapy.

The study will consist of a 4-week screening period, during which participants with prostate cancer will be screened for eligibility. On Day 1, all eligible participants will receive a single open-label administration of study intervention. Following treatment on Day 1, visits will occur on Day 3, Day 7, Day 29, Day 85, Day 141, Day 169 (second administration), Day 171, Day 175, Day 253, Day 309 and Day 337. (Note: if necessary, participants can request home visits, except for visits where study intervention is to be administered).

Participants will be considered to have completed the study when final procedures and assessments have been performed at the Day 337 visit. Participants who withdraw from the study before the completion of the Day 337 visit will have early discontinuation procedures and assessments performed at their final visit.

The study design is illustrated in [Figure 1](#).

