4 ANALYSIS SETS

Screened Set

The screened set will contain all participants who signed an informed consent for this study. In case of re-screening, the participant will be counted once only in the screened set. The previous site and assigned subject numbers will be collected to link the first and second screening data.

Enrolled Set

The enrolled set will contain all participants who were enrolled to study treatment. A participant will be considered as enrolled if he has signed the informed consent form and is assigned to treatment.

Intent-to-Treat Set

The intent-to-treat (ITT) Set will contain all participants who signed an informed consent form and received at least one administration of study intervention and have a serum testosterone level <1.735 nmol/L (50 ng/dL) on Day 1 (pre-dose measurement).

Full Analysis Set

The full analysis set (FAS) will contain all participants who signed an informed consent form and received two administrations of study intervention and completed all visits for testosterone measurement (Day 29, Day 85, Day 141, Day 169, Day 253, Day 309 and Day 337). Note, a participant will be included in the FAS if his testosterone measurement is ≥ 50 ng/dl before the end of treatment, end of study or withdrawn from study, whichever is earlier.

Per Protocol Set

The per protocol (PP) set will contain all participants from the FAS who did not experience any major protocol deviations that may interfere with efficacy evaluation (refer to section 5.3 for details regarding the management of deviations).

Safety Set

The safety set will contain all participants who receive at least one dose of study intervention.

Associated Procedure / Instruction Reference	319480-SOP
Form Reference	080091-FOR v7.0

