5.7.2.2 Primary Analysis

Primary analysis of castration maintenance rate will be based on the primary estimand in the FAS. Percentage of participants maintaining castrate levels of serum testosterone during the study along with the corresponding 95% exact CI will be provided in the FAS.

By-subject listing will be produced for all enrolled subjects.

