5.7.2.3 Sensitivity Analysis

Sensitivity analysis for the primary estimand is intended to assess treatment effects when using different strategies. Details are listed in the following.

Estimand ID	Primary-S1	Primary-S2	Primary-S3
Estimand	Primary	Primary	Primary
Analysis Type	Sensitivity	Sensitivity	Sensitivity
Analysis Set	ITT	ITT	ITT
Variable/Endpoint	Castration maintenance rate	Castration maintenance rate	Castration maintenance rate
Intercurrent Event	Strategy		
ICE1	Subjects will be included in the analysis regardless early withdraw status (Treatment policy)	Subjects will be included in the analysis regardless early withdraw status (Treatment policy)	Subjects will be included in the analysis regardless early withdraw status (Treatment policy)

Associated Procedure / Instruction Reference	319480-SOP
Form Reference	080091-FOR v7.0

IPSEN GROUP

CONFIDENTIAL

D-FR-52014-245

SAP Final: Version 1.0: 30 January 2023

PAGE 19/43

Estimand ID	Primary-S1	Primary-S2	Primary-S3
ICE2	With analysis window being applied, subjects without 2 consecutive missing testosterone value will be included in the analysis and subjects with at least 2 consecutive missing testosterone values will be considered as non-responders (Composite policy)	Without analysis window being applied, subjects without 2 consecutive missing testosterone value will be included in the analysis and subjects with at least 2 consecutive missing testosterone values will be considered as non-responders (Composite policy)	Analysis window is not applicable. Subjects with only one missing testosterone will be included in the analysis and available testosterone values will be analyzed as observed. For subjects with at least 2 missing testosterone values and without evidence of inadequate testosterone suppression (testosterone measurement ≥ 50 ng/dL), only testosterone values prior to the first missing will be included in the analysis. For subjects with at least 2 missing testosterone values and with evidence of inadequate testosterone suppression (testosterone measurement ≥ 50 ng/dL), available testosterone values will be analyzed as observed (Composite policy)
ICE3	Subjects will be included in the analysis regardless early treatment discontinuation status (Treatment policy)	Subjects will be included in the analysis regardless early treatment discontinuation status (Treatment policy)	Subjects will be included in the analysis regardless early treatment discontinuation status (Treatment policy)

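### ICE 2 and Primary-S1 to S3 do not limit missing testosterone values to the seven endpoint days; read literally, ICE 2 conflicts with the seven-day FAS and endpoint

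*SAP*

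**What the plan says.** Four places bear on which samples count.

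- **Endpoint (SAP 5.7.2.1).** Castration is required "at Day 29, Day 85, Day 141, Day 169, Day 253, Day 309 and Day 337, with two complete study intervention administrations". Seven days are named.
- **FAS (SAP section 4; Protocol 9.3 agrees).** A participant must have had both injections and "completed all visits for testosterone measurement (Day 29, Day 85, Day 141, Day 169, Day 253, Day 309 and Day 337"). These are the same seven days. A note keeps any man with a value of 50 ng/dL or more.
- **ICE 2 (SAP 5.7.2.1).** The event is "Subjects with at least one planned testosterone measurement missing on or prior to Day 337 without evidence of inadequate testosterone suppression". The handling is "The testosterone values of these participants will not be considered for the main analysis (principal stratum strategy"). No days are named.
- **Sensitivity analyses (SAP 5.7.2.3).** In Primary-S1 and S2, "subjects with at least 2 consecutive missing testosterone values will be considered as non-responders". In S3, for men with at least two missing values and none at or above 50 ng/dL, "only testosterone values prior to the first missing will be included in the analysis". Again no days are named.

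The primary analysis calls on both rules: "Primary analysis of castration maintenance rate will be based on the primary estimand in the FAS".

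The visits after the first injection include "Day 3, Day 7, Day 29, Day 85, Day 141, Day 169 (second administration), Day 171, Day 175" (Protocol 4.1). The schedule of activities plans a testosterone sample at each of them, so there are 11 planned post-dose samples: the seven endpoint days plus Days 3, 7, 171 and 175. The extra four feed a separate secondary endpoint. The window table in SAP 6.1 has a row for each of them.

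**The concern.** A missed Day 3 sample says nothing about castration on the seven days that define the endpoint. Yet if ICE 2 is applied as worded, it removes a man whose endpoint data are complete and castrate throughout. The removal is one-sided, because ICE 2 applies only where there is no value of 50 ng/dL or more. Failures therefore stay and only responders can be lost.

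The FAS rule and the ICE 2 rule then give different primary denominators, and nothing in the SAP says which prevails. In an open-label, single-arm trial, settling this after the data are visible would be a post hoc choice of denominator for the one analysis that decides the study. The same gap passes to S1, S2 and S3, and through SAP 5.7.3.2 and 5.7.3.4 to the 20 ng/dL analyses.

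**Working it through.** **1. The plan's own figure.** Inputs from SAP 2.3: null rate 90%, assumed rate 97%, n = 130, one-sided alpha 0.025, success if the exact 95% lower bound exceeds 90%. At n = 130 success needs at least 124 responders (at most 6 failures). Exact alpha is 0.0207 and power 0.903; 130/0.9 gives 145 after rounding up. The stated design reproduces.

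**2. How close the rule is.** Take six true failures and remove complete responders one at a time (Clopper-Pearson lower bounds):

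| Responders removed | Count | Lower bound | Result |
|---|---|---|---|
| 0 | 124/130 | 0.9022 | passes |
| 4 | 120/126 | 0.8992 | fails |

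The endpoint data are identical in both rows.

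**3. Chance of success under the literal reading.** The documents give no miss rate, so let m be an assumed, independent probability of missing each of the four extra samples among 130 otherwise evaluable men. Failures F ~ Bin(130, 0.03) are all kept. Retained responders R given F ~ Bin(130 − F, (1 − m)^4). Success means that the lower bound of R/(R + F) exceeds 0.90. Expected responders removed = 130 × 0.97 × [1 − (1 − m)^4].

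| m | Responders removed | Expected observed rate | Chance of success |
|---|---|---|---|
| 0 | 0 | 97.0% | 0.903 |
| 1% | 5.0 | 96.9% | 0.831 |
| 2% | 9.8 | 96.8% | 0.802 |
| 5% | 23.4 | 96.3% | 0.647 |

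**4. How much is one-sidedness.** Repeat step 3 but remove men regardless of outcome: n ~ Bin(130, (1 − m)^4), responders ~ Bin(n, 0.97). At m = 1% the chance of success is 0.849. Of the 7.2-point fall (0.903 to 0.831), about 5.4 points therefore come from smaller n and exact-test steps (power is 0.911 at n = 127 and 0.821 at n = 126), and about 1.8 from one-sidedness.

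**5. S1 and S2.** A man with all seven endpoint samples has two consecutive misses on the 11-visit list only if both Day 3 and Day 7, or both Day 171 and Day 175, are missing. With independent misses the probability is 1 − (1 − m²)². Among 145 men that is 0.03, 0.12 and 0.72 men at m = 1%, 2% and 5%. If S1 is read against the 90% bound with all 145 men, 138/145 gives 0.9031 and 137/145 gives 0.8942. One such man would lower the chance of clearing the bound from 0.928 to 0.856, and two would lower it to 0.740.

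The gap also works the other way. A man missing Day 169 and Day 253 has two consecutive misses on the seven-day list, but none on the 11-visit list if Days 171 and 175 were drawn.

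**6. S3.** A man missing both Day 3 and Day 7, with no value at or above 50 ng/dL, would keep no post-dose value even if all seven endpoint samples exist. He leaves the Kaplan-Meier estimate early; he is not scored as a failure.

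**The case against.** The best defence is context. ICE 2 sits directly under a variable that lists seven days. The protocol and SAP both spell out the FAS testosterone visits as those seven, and ICE 1 to 3 look like a restatement of the FAS conditions. On that view ICE 2 means the seven days and there is no conflict. This stands to the extent that a reader might infer an express rule to count all planned visits, and the SAP contains none. But the intended meaning has to be supplied by the reader. The word *planned* points to the schedule, and SAP 5.1.1.1 maps testosterone dates to the planned schedule through the 6.1 table, which includes the four extra days. A programmer could fairly count them.

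The size is also open to challenge, and much of that stands. The miss rates are assumed. Part of the power loss is exact-test discreteness. The bias runs against the drug, so it cannot manufacture a success. Keeping failures while excluding incomplete responders is built into the FAS note and would remain after the fix. One might suppose that the four extra visits are the easiest to miss because they are tied to fixed days. The documents do not show that: home visits are allowed on non-dosing days, and the 6.1 windows are wide (Days 2 to 5, Days 6 to 18, 1 to 4 days and 5 to 45 days after the second injection).

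On the sensitivity analyses, a reader might infer that one missed extra sample makes a man a non-responder, or that S3 scores missing data as failure. Neither is so: S1 and S2 need both samples after one injection to be missing, and S3 only truncates. Nor can S1 be said to turn negative, because the SAP gives it no success rule. With 10% drop-out planned, other missing data could in any case dominate S1.

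**Conclusion.** The concern holds as a conflict between rules. ICE 2 and S1 to S3 do not say which visits count as missing, and ICE 2 taken literally contradicts the seven-day FAS and endpoint. No figure in the documents is wrong.

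For the primary analysis the bias is small (at most 0.7 percentage points for m up to 5%) and conservative. The practical risk is a lost success in a design where a handful of excluded responders can decide the outcome: 0.90 falls to between 0.83 and 0.65 for m between 1% and 5%. That range rests on 130 otherwise evaluable men, a true rate of 97%, independent misses and assumed m. For S1 and S2 the effect is rare unless misses cluster around an injection, and it can go in either direction. For S3 it is early truncation only.

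**What to change.** In SAP 5.7.2.1, reword ICE 2 so that it is triggered by at least one of the seven endpoint-day measurements being missing (Day 29, 85, 141, 169, 253, 309, 337). In SAP 5.7.2.3, state for S1, S2 and S3 that a missing value, two consecutive missing values and the first missing value are all counted over those seven days only. Say the same in SAP 5.7.3.4 for the 20 ng/dL Kaplan-Meier estimate.

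The cost is SAP wording, with no new data and no change to the sample size. It should be settled before database lock. The change aligns ICE 2 with the FAS and the endpoint, and under it a man missing both Day 169 and Day 253 counts as having two consecutive misses in S1 and S2.

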5.7.2.2 Primary Analysis

Primary analysis of castration maintenance rate will be based on the primary estimand in the FAS. Percentage of participants maintaining castrate levels of serum testosterone during the study along with the corresponding 95% exact CI will be provided in the FAS.

By-subject listing will be produced for all enrolled subjects.

5.7.2.3 Sensitivity Analysis

Sensitivity analysis for the primary estimand is intended to assess treatment effects when using different strategies. Details are listed in the following.

Estimand ID	Primary-S1	Primary-S2	Primary-S3
Estimand	Primary	Primary	Primary
Analysis Type	Sensitivity	Sensitivity	Sensitivity
Analysis Set	ITT	ITT	ITT
Variable/Endpoint	Castration maintenance rate	Castration maintenance rate	Castration maintenance rate
Intercurrent Event	Strategy		
ICE1	Subjects will be included in the analysis regardless early withdraw status (Treatment policy)	Subjects will be included in the analysis regardless early withdraw status (Treatment policy)	Subjects will be included in the analysis regardless early withdraw status (Treatment policy)

Associated Procedure / Instruction Reference	319480-SOP
Form Reference	080091-FOR v7.0

IPSEN GROUP

CONFIDENTIAL

D-FR-52014-245

SAP Final: Version 1.0: 30 January 2023

PAGE 19/43

Estimand ID	Primary-S1	Primary-S2	Primary-S3
ICE2	With analysis window being applied, subjects without 2 consecutive missing testosterone value will be included in the analysis and subjects with at least 2 consecutive missing testosterone values will be considered as non-responders (Composite policy)	Without analysis window being applied, subjects without 2 consecutive missing testosterone value will be included in the analysis and subjects with at least 2 consecutive missing testosterone values will be considered as non-responders (Composite policy)	Analysis window is not applicable. Subjects with only one missing testosterone will be included in the analysis and available testosterone values will be analyzed as observed. For subjects with at least 2 missing testosterone values and without evidence of inadequate testosterone suppression (testosterone measurement ≥ 50 ng/dL), only testosterone values prior to the first missing will be included in the analysis. For subjects with at least 2 missing testosterone values and with evidence of inadequate testosterone suppression (testosterone measurement ≥ 50 ng/dL), available testosterone values will be analyzed as observed (Composite policy)
ICE3	Subjects will be included in the analysis regardless early treatment discontinuation status (Treatment policy)	Subjects will be included in the analysis regardless early treatment discontinuation status (Treatment policy)	Subjects will be included in the analysis regardless early treatment discontinuation status (Treatment policy)
ICE4	Same as primary estimand		
Population-level summary			
	Same as primary estimand	Same as primary estimand	Probability of Castration maintenance at Day 337 based on Kaplan-Meier estimate

